be considered an adverse event in the setting of normal subject values prior to taurine supplementation. Any intercurrent illness or injury that represents an exacerbation of pre-existing condition (e.g., increase frequency or severity) will also be considered an AE. In such cases it will be preferred to record the diagnosis as the AE rather than a series of terms relating to the diagnosis (e.g., worsening of asthma). An adverse drug reaction will be all noxious and unintended responses to taurine product. This means that a causal relationship between taurine and an AE is at least a reasonable possibility (i.e., the relationship cannot be ruled out).

The PI and one of the co-investigating MDs will determine the severity of the event and if the SAE or AE is related to the protocol using the categories noted below. Review of their determination will be sought from the Safety Officers. In the case of deferring opinions, higher grade of severity the more related rating will be accepted

Grade	Description
Mild	No limitation of usual activities
Moderate	Some limitation of usual activities
Severe	Inability to carry out activities

Not Related	The adverse finding was present prior to exposure to the investigational product, having the same or milder intensity OR The finding is considered likely to be related to an etiology other than the investigational product, that is, there is no evidence or arguments to suggest a causal relationship to the investigational product.
Possibly related	Exposure to investigational product and onset of the finding are reasonably related in time AND The adverse finding could be reasonably be explained by factors or causes other than exposure to investigational product.
Probably related	Exposure to investigational product and onset of the finding are reasonably related in time AND The adverse finding is more likely explained by exposure to investigational product than by other factors or causes.

SAEs will be reported to one of the co-investigator MDs as well as the Safety Officers, FDA, COMIRB, the CTRC within five working days of knowledge of the event. The participant's PCP will also be notified if deemed appropriate by the co-investigator MD. Unanticipated problems or events that result in an actual unforeseen harmful or unfavorable occurrence to the subject or others with also be reported to one of the co-investigating MDs within five working days of knowledge of the event. Information that indicates a change to the risks or benefits of the study will also be reported within five days of discovery to the Safety Officers,

FDA, COMIRB and CTRC. No new patients will be enrolled or studied until the SAE has been reviewed and appropriate action taken by the above listed bodies.

The PI will notify co-investigator MDs of abnormal safety monitoring lab results within five working days of resulted values. If deemed clinically appropriate by co-investigator MD, the subjects PCP will be notified. All other AEs will be logged and reported to COMIRB yearly or at the time of continuing review.

For full list of events to be reported to COMIRB see the Reportable Event Sheet to be used for monitoring and tracking individual events attached in Appendix V - Supplemental Materials.

A summary of data monitoring and reporting flow during the active portion of the study is noted below. A flow diagram of this information can be found in Appendix V - Supplemental Materials in the CTRC protocol application.

Pregnancy testing will be done on day 1, one day prior to the administration of taurine and reviewed by 5:00 PM that day. Positive test results will exclude the individual from participation in the study. A physical examination (to include blood pressure) and the Adverse Event Sheet Questionnaire will be completed on day 1 and just prior to taurine administration respectively. They will be repeated after administration of the last taurine dose. This data will be reviewed within 5 working days after the subject has completed the study protocol. Liver function study results that exceed two times the upper limit, triglycerides results that are greater than 400 mg/dl, and/or hypotension (blood pressure <90mmHg in adults or < the 5th percentile for age in children) as well as any clinically significant alteration in safety monitoring laboratory studies (as assessed by the co-investigating MD) that is present in two or more subjects in the setting of normal subject values before taurine supplementation will be reported to the co-investigators, FDA, COMIRB, CTRC, and Safety Officers within 5 working days of knowledge of this data. The protocol will be temporarily suspended pending review of collected data and recommendation about study continuance by Safety Officers, FDA, COMIRB and CTRC.

All unanticipated problems and unanticipated events will also be discussed with one of the co-investigating MDs within five working days of knowledge of the problem or event. Any identified trend in AEs will also be discussed within five working days of knowledge of the trend with one of the co-investigator MDs.

Compiled data will be examined for safety after 2, 4, and 8 subjects have completed the protocol and at the end of the study by the PI, co investigators and data Safety Officers. The PI, co-investigators and the data Safety Officers board will be looking for repeat adverse events (AEs) or trends in AEs.

SAEs will be reported to the study project manager, the PI or one of the lead site co-investigator MDs, FDA, COMIRB, local IRB as per their requirement, and the CTRC within five working days of knowledge of the event. In addition, the data Safety Officers and PI and co-investigators will convene within one week of reporting of a SAE.

C. Describe both subject discontinuation criteria and protocol stopping criteria:

With respect to the FMD studies, if an adult systolic blood pressure is < 105 mmHg or a child's blood pressure is < 10th percentile for age, nitroglycerin will not be administered. The subject will otherwise be maintained in the study.

With respect to the study in general, subject discontinuation criteria are as follows.

- Positive pregnancy test
- Any SAE that is possibly related to the study protocol.

Protocol stopping criteria are listed below. Such events will result in the study being temporarily suspended pending review of collected data and recommendation about study continuance by Safety Officers, FDA, COMIRB and CTRC.

- Any SAE that is possibly related to the study protocol.
- Liver function study results that exceed two times the upper limit, if triglycerides are greater than 400 mg/dl, and/or if hypotension (blood pressure <90mmHg in adults or < the 5th percentile for age in children) is present in two or more subjects in the setting of normal subject values before taurine supplementation.
- Any clinically significant alteration in safety monitoring laboratory studies, as assessed by the co-investigating MD and/or the Safety Officers that is present in two or more subjects in the setting of normal subject values before taurine supplementation.

Currently there is no funding source outside of the university, thus we do not expect an outside agent to have authority to suspend this trial, other than general regulatory authorities of the institution and the FDA in its general capacity to oversee drugs and food supplements. Actions that result in suspension or termination of the protocol, whether by COMIRB or some other entity, will be reported to the Pediatric General Clinical Research Center and the IRB verbally within 24 hours and via written documentation within 2 working days.

D. Plans for assuring data accuracy and protocol compliance:

The PI will conduct protocol compliance checks. Accuracy of the laboratory data related to safety is assured via use of Clinical Laboratory Improvement Amendments (CLIA) certified laboratory.

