Since inflammatory messengers such as TNF- α can stimulate osteoclasts without stimulating osteoblasts, long term elevation of TNF- α can cause osteoporosis. We will measure bone mineral density and will evaluate if the Z-scores are related to the inflammatory markers in particular to TNF- α . Such a finding would strengthen the development of a hypothesis of a possible relation, whereas its absence of such a relation would not necessarily negate this given the many parameters that can influence bone mineral density.

Finally, baseline pharmacokinetics of oral pharmacologic doses of taurine will be developed.

For safety reasons, the first two patients will be treated with a dose of 25 mg/kg/dose (maximum 1.5 g) twice daily. After review of safety parameters, the dose will then be increase to the planned dose of 75 mg/kg/dose (maximum 5 g) twice daily. The first four patients will be adults, before recruiting children in the study.

This short-term local pilot study will form the basis on which to later develop a national long-term study (orphan drug study), 4 years duration and placebo controlled, that will expand on the findings and include long-term variables such as those related to connective tissue and bone.

Primary Outcome Measure(s):

Oxidative stress and inflammation measures as follows:

- Luminex cytokine array studies to include the following cytokines
 - Interleukin 1-alpha (IL-1 α)
 - Interleukin 1-beta (IL-1 β)
 - Interleukin 1-ra (IL-1ra)
 - Interleukin 4 (IL-4)
 - Interleukin 8 (IL-8)
 - Interleukin 10 (IL-10)
 - TNF-alpha (TNF- α)
 - Monocyte Chemoattractant Protein-1 (MCP-1)
 - Interleukin 6 (IL-6)
 - Interleukin 12 (IL-12p70)
 - Interleukin 17 (IL-17)
 - MIP-1 α
 - MIP-1 β
- C-reactive protein (high sensitivity)
- Myeloperoxidase
- Transforming Growth Factor Beta (TGF- β)
- Extracellular superoxide dismutase
- TBARS
- ELISA Assay
 - Interleukin 1-alpha (IL α)
 - Interleukin 1-beta (IL- β)
 - Interleukin 10 (IL-10)
 - TNF-alpha (TNF- α)
- 8-Isoprostane metabolites (2,3-dinor-F₂-IsoPs combined signal) of 8-isoPGF_{2 α} , urine
- Dityrosine, urine
- Glutathione reduced (GSH) and oxidized (GSSG) in whole blood

Vascular coagulability markers:

- Endothelial Function as assessed by brachial artery flow-mediated dilation (FMD): percent change induced by hypoxemia in brachial artery diameter and flow measurement (derived from diameter and flow velocity)

- Platelet aggregation

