
The above biomarkers and disease-related metabolites will be further related to the clinically relevant vascular endothelial function studied via a standardized doppler method available through the UCH CCTSI. Brachial artery flow-mediated dilation (FMD) will be used as a non-invasive measure of endothelial dependent dilatation (EDD), mediated in part by nitric oxide (Liao et al, 1991) (Dakak et al, 1998). Ultrasound measurements of

brachial artery EDD (i.e., FMD studies) during forearm reactive hyperemia and in response to sublingual nitroglycerine (0.4mg), well-established measures of vascular endothelium-dependent and -independent vasodilatation, respectively, will be performed as previously described (Celermajer et al, 1992) (Eslerza et al, 2004). This entails ultrasound measurement of brachial arterial diameter in the resting state, followed by occlusion of the brachial artery by a blood pressure cuff for 5 minutes. The cuff is then rapidly deflated. The ensuing turbulent blood flow results in endothelial shear stress. This activates a cascade of endothelial mediated events resulting in dilation of the vessel. The dilation is quantified by ultrasound. The maximum percent increase in vessel size after the release of the blood pressure cuff, or FMD, is a measure of endothelial-dependent vasodilatation. Following this, endothelial-independent vasodilatation is assessed. Brachial artery ultrasound measurements are again obtained in the resting state. Following this, 0.4 mg of nitroglycerin, source being Nitrostat SL tablets, is given sublingually. Nitroglycerin will not be used in patients under age 18 years. Nitric oxide is produced from the nitroglycerin without need for the endothelial cells. The nitric oxide has a direct vasodilator effect. Brachial artery diameter is again assessed via ultrasound. The maximum percent increase in vessel size after the nitroglycerin is as a measure of nitrate-mediated, endothelium-independent vasodilatation. Abnormal FMD results in the setting of normal endothelial-independent vasodilatation results suggest endothelial dysfunction. To avoid confounding variables subjects will be asked not to eat 4 hours prior to study or consume caffeine 10 hour prior to study .

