The above biomarkers and disease related metabolites will be also related to clinically relevant platelet function studies. We hypothesize that the inflammatory and oxidant environment pushes normal platelets into a chronic low-grade aggregation status, and that this improves with taurine. We will measure urinary 11-dehydroTXB2 and 2,3-dinor-TXB2 to reflect aggregation status, and in vitro platelet aggregation studies to reflect the platelet function. The metabolites 11-dehydroTXB2 and 2,3-dinor-TXB2 have been reported as elevated in CBSDH patients.

Following the observational studies, participants will be treated with oral taurine 75 mg/kg (maximum 5 grams) BID for 4 ½ days. The first two patients will be treated with a dose of 25 mg/kg (maximum 1.5 g) twice daily, before increasing the dose to the full study dose. USP grade taurine supplied by Solace Nutrition, lot number 6608 (Solace Nutrition, [name]) and Medisca Inc, lot number 105927 (Medisca Inc, [name]) will be used. If for any reason this lot number changes, we will submit additional Certificate of Analysis to the FDA and COMIRB for the new lot numbers. Participants will be weighted on visit day one. Based on the patient weight, a prescription order will be written by the MD Co-investigator or CTRC nurse practitioner for taurine and will be given to The Children's Hospital Pharmacy Investigational Drug Services. Individual, single dose packets will be weighed and dispensed by the pharmacy to the Clinical and Translational Research Center (CTRC). Each single dose packet will be labeled with the study medication name and dose. The amount of product needed for the first 4 days of the study period will be dispensed up front in a container that is labeled with subject's name, medication name, medication dose, and directions for administration. Based on the prescription order, the Children's Hospital Pharmacy will dispense the medication to the inpatient Clinical and Translation Research Center (CTRC). The first dose of study medication will be administered orally to the study patient by a RN. The RN will mix taurine with 150mls of water or the individual's favorite juice. The RN

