will review administration instructions and observe intake of the first oral dose. There after the medication will be self administered by the participant in the same manner; the patient will be instructed that once taurine is mixed with a liquid it must be consumed within thirty minutes of mixing. The last dose will be dispensed in a separate container by the Investigational Pharmacy to the outpatient CTRC with labeling and administration as that described above.

Disease metabolites and biomarkers of oxidative stress and inflammation laboratory studies will be obtained at 4 hours after the first dose, and after completion of 4 days of treatment. Comparison of results prior to treatment with results after one dose and after 4 days of treatment will be done. Functionally relevant platelet aggregation will be obtained after 4 days of treatment. Functionally relevant FMD studies will be obtained after the blood work and the last taurine dose, this being after 4 ½ days of treatment. After the blood flow studies have been completed, the patient will be discharged. Comparison of results prior to treatment and results after treatment will be done.

Pharmacokinetic studies will be done after the first dose with blood samples obtained before administration (time 0), and after 30 min, 1, 2, 4, 6, 8, and 12 hours. A steady state level will be obtained after 4 days treatment. Plasma samples will be spun down immediately to avoid platelet aggregation, and samples stored at – 70 degrees Celsius until analysis (to prevent hypotaurine from oxidation to taurine). Sample will be analyzed using an LC- MS/MS system in combination with online extraction (LC/LC-MS/MS by [name], and pharmacokinetic results modeled using SAAM II (University of Washington) by Drs. [name] and [name].

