It is anticipated that the biomarkers of oxidative stress and inflammation will be increased above the norm in participants and the degree of elevation will be related to Hcy levels. A decrease in the elevation of the biomarkers is anticipated following treatment with taurine. It is also anticipated that FMD studies will be abnormal in participants and that improvement will be seen following taurine supplementation. We anticipate that platelet aggregation studies will be normal, but that markers of generalized activation of platelets, thromboxane B2 metabolites, are elevated, and will reduce with treatment. Bone mineral density Z-scores will be related to baseline TNF- α levels.

J. Potential Problems:

1. Recruitment: Given the rarity of the disorder, our potential participant sample volume is low. Geographic and economic issues may make it difficult for some

potential subjects to participate in the study. Low participation in the study might impact the statistical analysis of data. Should insufficient patients be recruited locally, then advertisement through national organization will be done to increase participation. Of note, while there is one report of Vitamin C supplementation ameliorating endothelial dysfunction in individuals with CBSDH, its use has not been widely investigated and use of Vitamin C to treat homocystinuria is not standard of care. We therefore do not anticipate this excluding criteria to markedly effect recruitment.

Patients with prescribed salicylate (such as Aspirin) therapy will not have this discontinued but will be excluded from the platelet function studies. We anticipate that this will impact up to 25% of the recruited population. A recruitment of 12 patients will likely provide a minimum of 8 patients in which this clinically relevant measure can be analyzed. Should the percentage of patients taking platelet aggregation inhibitors exceed our anticipated number, then we will plan to extend the study to increase the number of patients to be enrolled. Similar considerations are for use of cGMP phosphodiesterase 5 inhibitors (such as Viagra) and exclusion of FMD studies, although we doubt that the rate of patients taking this medication in our young age group would be as high as 25%. Overall, our goal is to recruit 8 patients that participate in all aspects of the study and are treated at the target dose of 150 mg/kg/day (maximum 10 g/day).

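### The protocol does not provide for FMD scans to be read blind to visit, although the comparison is open-label, uncontrolled and before/after, with improvement expected

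*Combined protocol and SAP*

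**What the plan says.** Section 5.G describes FMD as "studied via a standardized doppler method available through the UCH CCTSI", carried out as in cited papers. On measurement it says "The dilation is quantified by ultrasound", and it defines the readout: "The maximum percent increase in vessel size after the release of the blood pressure cuff, or FMD, is a measure of endothelial-dependent vasodilatation".

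The schedule in Section 5.H places one endothelial study on Day 1 and one on Day 6. For the second, Section 5.G says "Functionally relevant FMD studies will be obtained after the blood work and the last taurine dose", and then "Comparison of results prior to treatment and results after treatment will be done". Section 5.K (II.C) specifies a paired t-test of the change against zero and states neither direction nor significance level for FMD.

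Treatment is open: "Each single dose packet will be labeled with the study medication name and dose". A placebo appears only in the description of a later study, "4 years duration and placebo controlled" (Section 5.A). The Expected Results section anticipates that FMD will be abnormal at baseline and that "improvement will be seen following taurine supplementation".

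FMD is listed under the primary outcome measures in Section 5.A. Section 5.K names only TBARS and TNF-α as primary efficacy parameters and handles FMD under secondary, exploratory measures.

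**The concern.** FMD is a ratio of ultrasound diameters. The numerator uses the largest diameter found after cuff release and the denominator is the resting diameter. If any part of the reading involves judgement, a reader who expects improvement could shift the later scan relative to the earlier one. In a trial with a concurrent control arm and masked allocation, such a shift would affect both arms and largely cancel. Here each patient is his or her own control and the order is always before, then after, so nothing in the design cancels it.

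The plan takes care over other sources of FMD variation: fasting and caffeine before the scan, exclusion of uncontrolled hypertension, and hormone levels for menstrual timing. It describes no comparable safeguard for the reading. At stake is the credibility of one of the few functional results of a pilot that is meant to form the basis of a longer placebo-controlled study.

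**Working it through.** **1. What the text does and does not provide.** I looked for masked, offline, central, coded or duplicate reading of FMD in the procedure and timing (5.G), the visit schedule (5.H) and the analysis (5.K). None is mentioned. Equally, nothing states that the reader knows the visit.

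**2. The plan's own paired calculation.** Section 5.K gives power for 8 pairs with a one-sided 5% paired t-test. It concerns TNF-α and TBARS; no power figure is given for FMD. With effect size d in SDs of the change, n pairs and n − 1 degrees of freedom, power = P(T > t_crit), where T is noncentral t with noncentrality d√n. For n = 8 there are 7 degrees of freedom and t_crit = 1.895.

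| d | d√8 | Power, recomputed | Power, plan |
|---|---|---|---|
| 0.98 | 2.77 | 80.1% | 80% |
| 1.15 | 3.25 | 89.8% | 90% |
| 1.30 | 3.68 | 95.0% | 95% |

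The table reproduces, so the same formula can be applied to a reading shift.

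**3. False-positive rate under a reading shift.** Set the true effect to zero and let the second scan be read higher by a constant b, in SDs of the paired change. The chance of significance is P(|T| > t_crit) with noncentrality b√n.

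Inputs:
- n = 8 is the minimum evaluable number on high dose, and also the goal for patients taking part in all aspects (5.J, 5.K). n = 10 is the upper figure for evaluable patients in 5.K.
- The test is taken as two-sided at 5%. This is an assumption, because 5.K gives no direction or level for FMD.
- b is an assumption. The documents give neither an FMD SD nor a reading error. A shift of 0.5 to 1.0 percentage point with an SD of the change of 2 to 3 points gives b from 0.5/3 = 0.17 to 1.0/2 = 0.50.

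Critical values are 2.365 (n = 8) and 2.262 (n = 10).

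| b (SD of change) | n = 8 | n = 10 |
|---|---|---|
| 0 | 5.0% | 5.0% |
| 0.10 | 5.7% | 5.9% |
| 0.17 (0.5/3) | 7.0% | 7.6% |
| 0.25 (0.5/2) | 9.4% | 10.9% |
| 0.33 (1.0/3) | 13.0% | 15.7% |
| 0.50 (1.0/2) | 23.2% | 29.3% |

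The rate rises with n at a fixed b, because more patients estimate the shift more precisely and do not reduce it. Masked reading that removes the shift returns the rate to 5%.

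**The case against.** The strongest reply is that the documents are silent and do not show unmasked reading. A reader might infer from the fixed order of scans and the open treatment that whoever quantifies FMD knows which scan follows taurine. The text does not support that as fact. Section 5.G refers to a standardised method at a shared research facility and to cited papers that cannot be consulted here. Reading may be offline, automated or already masked. This part of the objection stands, and the point is therefore confined to what the protocol fails to provide for.

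A reader might also infer that masking is the only safeguard available. It is not. Automated edge detection or duplicate reading would help, and in adults the nitroglycerin response could reveal a general tendency to read later scans high. That check is partial, since minors and some adults do not receive nitroglycerin.

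Third, larger false-positive rates follow if a one-sided 5% test is assumed (up to 35.7% at n = 8 and b = 0.5). The one-sided level in 5.K belongs to the TNF-α and TBARS power calculation, and the FMD test is stated without direction, so the two-sided figures are the fair ones. At their low end the rise is about two percentage points.

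Fourth, FMD is analysed as secondary and exploratory, which limits the stakes. This also stands, although Section 5.A still lists FMD as a primary outcome measure.

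None of this supplies the missing safeguard. If masked reading is already the practice, writing it into 5.G costs almost nothing.

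**Conclusion.** The concern holds as a gap in the plan: no provision is made for FMD to be read blind to visit, in a design where a systematic reading shift cannot be separated from a treatment effect. Under the assumed shifts of 0.17 to 0.5 SD, the two-sided 5% error rate becomes about 7-23% with 8 patients and 8-29% with 10. With a shift of 0.1 SD it stays near 6%, so a very small bias would do little harm. These figures illustrate sensitivity. They do not estimate bias in this trial, for which the documents give no basis.

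The change is worth making because it is cheap and protects a functional outcome. It does not affect the TBARS and TNF-α analyses.

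**What to change.** Add to Section 5.G:
- Day 1 and Day 6 FMD images are stored with date and visit removed.
- After the second scan, the site's existing reader measures both scans of a patient in random order without knowing the visit.
- Both values are locked before the visit is unmasked.

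The cost is storing and coding the images. The protocol does not describe current image storage or name the reader at each site, so each recruiting site would need to confirm both. No extra scan or reader is intended.

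The downside is that baseline FMD is not read on the day. I found no decision in the protocol that waits on that value; withholding nitroglycerin on the day depends on blood pressure (Section 8.C).

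Masked reading leaves two problems untouched: bias in acquiring the images, since the operator may know the visit, and any change over time unrelated to taurine. Both should be acknowledged when the FMD result is reported.
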